### 3.3. Treatment

#### 3.3.1. Investigational Therapy

Patients who have provided written informed consent will undergo screening procedures. Once eligibility is established patients will begin therapy with Pasireotide LAR 40 mg.

Pasireotide LAR 40 mg will be administered as intra-muscular (i.m.) intragluteal injections every 4 weeks. Uptitration will occur to Pasireotide LAR 60 mg after 6 months of therapy with Pasireotide LAR 40 mg if POMC level has not been suppressed and/or pituitary tumor shrinkage has not occurred. For patient receiving 40 mg dose down-titration to 20 mg is permitted for patients who do not tolerate 40 mg. For patients who are up-titrated to the 60 mg dose down-titration to 40 mg is permitted if tolerability issues occur on this higher dose.

Medication labels will comply with legal requirements and be printed in English. The storage conditions for study drug will be described on the medication label.

Should anti-diabetic treatment be needed during the study (see adverse events) this will be provided by the investigator according to standard clinical practice for diabetes care. The order of initiation of anti-diabetic therapy is expected to be, but is not prescribed as part of this protocol:

- Metformin at individual doses starting from 1000 mg/day to maximum dose according to the approved package insert and depending on the patient tolerability
- Sitagliptin 50 or 100 mg administered orally once a day

- Insulin administered s.c. according to package insert

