#### Adverse events

Information about all adverse events, whether volunteered by the subject, discovered by investigator questioning, or detected through physical examination, laboratory test or other means, will be collected and recorded in study-specific source documents and followed as appropriate. An adverse event is any undesirable sign, symptom or medical condition occurring after starting study drug (or therapy) even if the event is not considered to be related to study drug (or therapy). Study drug (or therapy) includes the drug (or therapy) under evaluation, and any reference or placebo drug (or therapy) given during any phase of the trial.

Medical conditions/diseases present before starting study treatment are only considered adverse events if they worsen or become more frequent after starting study treatment. Adverse events occurring before starting study treatment but after signing the informed consent form will be recorded in the subject records. Abnormal laboratory values or test results constitute adverse events only if they induce clinical signs or symptoms or require therapy, and will be recorded in study-specific Adverse Events source documents.

As far as possible, each adverse event will also be described by:

1. its duration (start and end dates),
2. the severity grade (mild, moderate, severe)
3. its relationship to the study drug (suspected / not suspected),
4. the action(s) taken and, as relevant, the outcome.

Guidelines for treatment of patients experiencing AEs (Per CTCAE V4.03)

Medication	Adverse event	Action
Pasireotide LAR i.m.	AE CTC grade $\leq$ 2	No drug adjustments

Medication	Adverse event	Action

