	AE CTC grade $\geq 3$ and assessed as study drug related	
Reduce pasireotide LAR i.m. dose by 20 mg. If the AE improves to grade <math>\leq 2</math> before the next administration, increase dose back to the prior dose. If the dose is increased and the AE recurs at a grade <math>\geq 3</math>, the dose should be reduced back to 20 mg. Down-titration should proceed similarly if patients have been uptitrated to 60 mg per month with down-titrations proceeding from 40 mg and then to 20 mg as indicated. The patient should stay on this lower dose if clinical benefits are maintained.
 
If the AE does not improve to grade <math>\leq 2</math>, the dose is to be reduced further if clinical benefits are maintained. If the AE does not improve to grade <math>\leq 2</math> on the minimum study dose, the treatment should be stopped. The patient should be discontinued and followed up for safety.

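### The triggers for dose reduction conflict between Section 3.3.1 and the adverse event table, and the table is ambiguous on recurrence at 60 mg and on the minimum dose

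*Combined protocol and SAP*

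**What the plan says.** **Section 3.3.1, Investigational Therapy.** For the starting dose: "For patient receiving 40 mg dose down-titration to 20 mg is permitted for patients who do not tolerate 40 mg". For the higher dose: "For patients who are up-titrated to the 60 mg dose down-titration to 40 mg is permitted if tolerability issues occur on this higher dose". Neither sentence names a CTC grade or requires the event to be attributed to the drug. The section states no minimum dose and no rule for stopping.

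**Section 3.4.2, Adverse events, guidelines table.** At grade 2 or below the action is "No drug adjustments". For events of grade 3 or above that are judged drug related, the first action is "Reduce pasireotide LAR i.m. dose by 20 mg". If the event improves before the next injection, the earlier dose is restored. If it then recurs at grade 3 or above, "the dose should be reduced back to 20 mg. Down-titration should proceed similarly if patients have been uptitrated to 60 mg per month"; the second of these sentences goes on to describe a path through 40 mg and then 20 mg. Treatment stops if the event does not improve to grade 2 or below on the minimum study dose, a term that is given no value in mg.

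**Section 3.4.2, Hyperglycemia.** A fasting glucose above 250 mg/dL leads to a lower dose, with neither the size of the step nor a floor given. Treatment is discontinued if fasting glucose is 240 mg/dL or more, or HbA1c 10% or more, despite dose reduction. The number of reductions to be tried first is not stated.

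**The concern.** Two sections govern the same decision and use different triggers. An investigator who follows Section 3.3.1 may lower the dose for a mild or moderate event that the patient tolerates poorly; one who follows the table leaves it alone. The case is foreseeable. Section 1.2.1.1.1 reports, for pasireotide LAR in the trial in medically naïve acromegaly, diarrhea in 33.1% of patients against 0.6% at grade 3 or 4, and hyperglycemia in 28.1% against 2.2%. Most such reactions were therefore below grade 3. Those patients had a different disease, and the figures do not show how many found the event hard to tolerate.

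The first thing at stake is patient safety and uniform conduct. The second is interpretation. In an open-label study of 10 patients without a control group, the dose a patient is receiving at 12 months would depend partly on which text was followed, so the pooled change in POMC would come from a mix of doses that the protocol does not determine.

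**Working it through.** There is no figure in the plan to reproduce. The check sets the dose paths side by side, by current dose and by type of event.

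| Situation | Section 3.3.1 | AE table, Section 3.4.2 | Result |
|---|---|---|---|
| 40 mg, first drug-related grade ≥3 event | 20 mg permitted | 40 − 20 = 20 mg | Agree |
| 60 mg, first drug-related grade ≥3 event | 40 mg permitted | 60 − 20 = 40 mg | Agree |
| 40 mg, poorly tolerated grade ≤2 event | 20 mg permitted | Stays at 40 mg | **Conflict** |
| 60 mg, poorly tolerated grade ≤2 event | 40 mg permitted | Stays at 60 mg | **Conflict** |
| 40 mg, recurrence after re-escalation | 20 mg permitted | 20 mg | Agree |
| 60 mg, recurrence after re-escalation | 40 mg permitted | 20 mg, or 40 mg first | **Ambiguous within the table** |
| Dose at which persistence means stopping | No rule | Minimum study dose, no value | **Undefined** |

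1. *Trigger.* The table has two rows: grade ≤2, and grade ≥3 with relatedness. Section 3.3.1 has one criterion, tolerability. They diverge wherever an event is poorly tolerated but is grade 2 or lower. Neither section refers to the other or says which takes precedence.

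2. *Recurrence at 60 mg.* The sequence is 60 mg, then 40 mg, improvement, back to 60 mg, recurrence. Taken literally, the recurrence sentence names a fixed dose of 20 mg. Returning *back* to 20 mg fits a patient who had previously been reduced from 40 mg to 20 mg; it does not fit one whose only reduced dose was 40 mg. The following sentence, which applies the scheme to 60 mg by analogy, gives 40 mg first and 20 mg only if needed. Both readings come from the same table cell.

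3. *Floor.* The lowest dose named in either section is 20 mg, but neither identifies it as the minimum study dose. Stopping depends on that term.

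4. *Hyperglycemia.* This rule calls for a decrease without a step size, so it cannot resolve items 2 and 3, and it needs to match whatever is adopted.

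**The case against.** The best defense is that Section 3.3.1 is permissive and the table is headed as guidelines. The table would then be the default and Section 3.3.1 would leave room for judgment. The sentence on 20 mg can likewise be taken as addressing patients who started on 40 mg, with the next sentence adapting it for 60 mg. This makes the intended scheme easier to guess, and the agreement on the first step for drug-related grade ≥3 events stands in full. It does not remove the difference at grade ≤2, because no order of precedence is given, and it supplies no value for the minimum dose.

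Two stronger readings are tempting, and the documents support neither.

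- *A reader might infer that the sections set different minimum doses and stopping points, 40 mg against 20 mg, for patients who reached 60 mg.* That requires the words "up-titrated to the 60 mg dose down-titration to 40 mg is permitted if tolerability issues occur on this higher dose" to be a floor. The sentence gives permission and does not limit the reduction to that one step. The separate sentence for patients receiving 40 mg can cover someone who has come down from 60 mg, and the path is then 60, 40, 20 in both sections. Section 3.3.1 has no stopping rule that could conflict with the table's.

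- *A reader might infer lost patients and lost power.* Under the table, recurrence leads to a reduction; stopping follows only from failure to improve on the minimum dose. Nothing in the documents ties this wording to a number of discontinuations. Nor does stopping treatment automatically remove a patient from the paired comparison, since Section 4.1 analyzes the change to the final study visit.

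**Conclusion.** The concern holds in a limited form. There is one direct conflict between sections: whether a poorly tolerated grade ≤2 event allows a reduction, at 40 mg and at 60 mg alike. There are two defects within the table: the dose after a recurrent grade ≥3 event in a patient re-escalated to 60 mg (20 mg or 40 mg), and a minimum study dose without a value. For a first drug-related grade ≥3 event the sections agree, and no conflict in stopping rules between them is shown.

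The size is qualitative. In the situations marked above, the next dose differs by 20 mg between readings; how often those situations will arise among 10 patients cannot be derived from the documents. The conclusion assumes that poor tolerance in Section 3.3.1 can include events of grade 2 or lower, which its wording does not exclude. Which rule is clinically right is not judged here. This is a safety-relevant inconsistency that should be corrected; it does not show a fault in the sample size or the primary analysis.

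**What to change.** Reconcile Section 3.3.1, the AE guidelines table and the grade 3 hyperglycemia rule in Section 3.4.2 into a single dose-modification table. It should be organized by current dose, AE grade, relatedness, and first occurrence or recurrence, and should state the minimum study dose in mg. Section 3.3.1 and the hyperglycemia text should then refer to that table and not carry rules of their own. The clinical team decides every value and trigger.

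The cost is a change of wording only, with no new assessments and no change to the sample size. Because it concerns dosing it is not merely administrative, so under Section 5.1 it needs a written amendment approved by the IRB.

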## SPECIAL MONITORING FOR ADVERSE EVENTS

### QT

- **QT 480 msec < QTcF  $\leq$  500 msec**

If at any visit a 480 msec < QTcF  $\leq$  500 msec is observed for a first time for a patient at a given dose level, the following steps will be taken. A cardiology consultation will be sought as soon as practical but within 7 days of the initial finding of abnormal ECG and the cardiologist must re-evaluate the ECG. The study treatment will be postponed until a cardiologist has re-evaluated the ECG.

- If a QTcF > 480 msec is NOT confirmed, no further action needs to be taken.
- If a QTcF > 480 msec is confirmed, a cardiologist must perform a thorough examination (such as reviewing baseline ECG, concurrent medications and performing a cardiovascular examination, including at least a cardiac auscultation) to assess the patient for cardiovascular risk factors.
- If based upon the assessment by the cardiologist, the investigator considers that there is an acute cardiovascular safety risk and that the patient should not continue with study medication, the patient will be discontinued immediately (discontinuation criteria to be followed).
- If following the examination by the cardiologist, the investigator considers that there is no acute cardiovascular safety risk the patient can continue to receive study medication.

- **QTcF > 500msec**

If at any visit a QTcF > 500msec is observed, the following steps need to be taken:

- Triplicate ECGs, each 2-3 minutes apart, need to be taken approximately 1 hour after the initial ECG. The mean QTcF from the triplicate ECGs will be determined. If

the mean QTcF is > 500msec, the patient has to postpone study treatment until a cardiologist has re-evaluated the ECG. The re-evaluation needs to be done as soon as practical but within 7 days of the initial finding of abnormal ECG.

- If the cardiologist confirms a mean QTcF > 500msec, the patient has to be withdrawn from the study.
- Otherwise and if the cardiologist confirms that at least one ECG shows a QTcF > 480msec, the cardiac assessments described for a confirmed QTcF > 480msec need to be followed.

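### After a first QTcF above 500 ms, a triplicate mean of 500 ms or less can leave dosing with no written hold, although a first reading of 485 ms always gets one

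*Combined protocol and SAP*

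**What the plan says.** The QT part of the special monitoring rules in section 3.4.2 has two branches.

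- **Above 480 and up to 500 ms.** When such a value "is observed for a first time for a patient at a given dose level, the following steps will be taken". These include a cardiology consultation within 7 days and an unconditional hold: "The study treatment will be postponed until a cardiologist has re-evaluated the ECG". If a value above 480 ms is confirmed, the cardiologist examines the patient. If afterwards "the investigator considers that there is no acute cardiovascular safety risk the patient can continue to receive study medication".
- **Above 500 ms.** The first step is a same-visit check: "Triplicate ECGs, each 2-3 minutes apart, need to be taken approximately 1 hour after the initial ECG". The hold comes next and is conditional. It applies if "the mean QTcF is > 500msec, the patient has to postpone study treatment until a cardiologist has re-evaluated the ECG", again with 7 days for the re-reading. A mean above 500 ms that the cardiologist confirms leads to mandatory withdrawal. The last bullet covers the remainder: "Otherwise and if the cardiologist confirms that at least one ECG shows a QTcF > 480msec", the assessments from the lower branch apply. That bullet mentions neither a postponement nor a time limit.

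The general adverse-event rules in the same section add no hold pending review. "Abnormal laboratory values or test results constitute adverse events only if they induce clinical signs or symptoms or require therapy", and for a drug-related event of grade 3 or higher the first action is "Reduce pasireotide LAR i.m. dose by 20 mg".

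**The concern.** A safety rule should be at least as protective after a worse first reading as after a milder one. Here a single first reading of 485 ms stops dosing until a cardiologist has looked at it. A single first reading of 520 ms may not, because its hold depends on the triplicate mean and the lower branch stops at 500 ms. The site would have to infer the hold from the order of the assessments.

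A value above 500 ms is more than 50 ms over the male entry limit of 450 ms and more than 40 ms over the female limit of 460 ms (exclusion criterion 6). The product is a monthly depot with a half-life of about 16 days (section 1.2.1.1.1), so an injection given before review cannot be taken back. In the visible part of the visit table, scheduled ECGs fall at V1 to V4, V7, V10 and V14, while injections are monthly. Several further doses could therefore precede the next scheduled ECG.

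**Working it through.** The plan gives no figure to reproduce here. The check applies the two written holds literally to example readings.

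**Inputs (section 3.4.2, QT):**

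- Hold A: 480 < QTcF ≤ 500 ms, first such finding at that dose level.
- Hold B: initial QTcF > 500 ms and triplicate mean > 500 ms.
- Triplicate mean = (r1 + r2 + r3) / 3.
- A reading of exactly 480 ms is outside Hold A, because the lower bound is strict.

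The example readings below are illustrative and are not trial data.

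| Initial ECG (ms) | Triplicates (ms) | Mean (ms) | First 480-500 ms finding at this dose level | 480-500 ms finding already seen at this dose level |
|---|---|---|---|---|
| 485 | not required | n/a | held (A) | no step written |
| 520 | 503/505/507 | 1515/3 = 505.0 | held (B) | held (B) |
| 520 | 490/492/494 | 1476/3 = 492.0 | held (A) | no written hold |
| 520 | 478/480/479 | 1437/3 = 479.0 | no written hold | no written hold |
| 520 | 475/510/510 | 1495/3 = 498.3 | held (A) if the mean counts as a finding; no written hold if only individual readings count | no written hold |

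**Comparing first events.** Rows 1 and 4 show the inconsistency: 485 ms is held, while 520 ms with no triplicate value above 480 ms is not. Row 5 is clinically less comfortable, because three of the four ECGs that day exceed 500 ms. Whether it is held depends on whether a mean can be an observed finding, which the text does not say.

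**Comparing repeat events.** In the last column, a 520 ms event with a mean of 500 ms or less has no written hold, but a repeat 485 ms has no written step at all. The higher reading still gets triplicates and, through the last bullet, implied cardiology review. So there is no inversion between repeat events. What remains is a narrower gap: the earlier cardiology review was of a value between 480 and 500 ms and did not cover one above 500 ms.

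**Does the last bullet supply a hold?** The initial ECG above 500 ms can itself be the one ECG the cardiologist confirms above 480 ms, so all these cases can reach the bullet. It leads to an examination after which treatment may continue, which implies that continuing waits for the examination. However, the only sentence in that branch that sends an ECG to a cardiologist, with its 7-day limit, is conditional on a mean above 500 ms. If the bullet is read as applying only after that step, even the referral is unspecified for a lower mean. Neither reading writes down a hold or a deadline.

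**Other places checked.** The adverse-event definition and dose-reduction table in section 3.4.2 do not postpone dosing pending review. The discontinuation rules in section 3.3.2 list an abnormal test result as a possible reason to stop, but contain no QT hold.

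**The case against.** The strongest reply is that the plan already has the substance and lacks only the word. A triplicate within about an hour is a sensible confirmation step. If three repeats fall at or below 480 ms, the first value may well have been spurious. The last bullet puts cardiology assessment before continuation, and a confirmed mean above 500 ms is both held and followed by withdrawal. Limiting the automatic hold to a first 480-500 ms finding is a visible choice, since the patient's earlier ECG will have been re-read. The investigator may also act on an abnormal ECG without declaring an adverse event.

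Most of this stands, and it sets the weight of the point. It does not supply a hold or a deadline when the mean is 500 ms or less. Nor does it explain why an unconfirmed 485 ms is held while an unconfirmed 520 ms is not.

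Three stronger readings are tempting, and the documents do not support them:

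- A reader might infer that every mean of 500 ms or less escapes a hold. It does not, because the 480-500 ms rule catches a value in that range the first time it is seen at that dose level.
- A reader might infer that such patients would be dosed without cardiology review. The last bullet implies the opposite.
- A reader might infer that higher readings are less protected in general, including repeat events. Among repeat events they are not.

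Counting how many branches lack a hold would also say nothing about how often this occurs or how dangerous it is.

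**Conclusion.** The point holds as a gap in explicit wording, clearest between first events: 485 ms is always held, and 520 ms with no triplicate reading in the 480-500 ms range has no written hold. The repeat-event case is a lesser gap, not an inversion.

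The practical effect cannot be quantified. Section 1.2.1.1.1 names QT prolongation among the reactions seen but gives no rate, and with 10 patients the situation is likely rare. The effect also depends on whether the ECG is taken before the injection at a visit, which the available text does not show. If the injection comes first, the next dose is about 28 days away, and a review completed within 7 days would make a hold moot.

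The conclusion assumes a literal reading of the QT rules. For mixed triplicates such as 475/510/510 in a first event, it further assumes that only individual readings count. No endpoint, sample size or analysis is affected. This is a cheap safety improvement of low practical weight, worth making because a depot dose cannot be recalled.

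**What to change.** Replace the conditional hold in the above-500 ms branch with a rule along these lines: any QTcF above 500 ms defers the next dose, whatever the triplicate mean and whatever was found before at that dose level, pending a cardiologist's re-reading of the initial and triplicate ECGs, to be completed within 7 days of the initial ECG. Keep mandatory withdrawal for a cardiologist-confirmed mean above 500 ms, and keep the assessments for a confirmed value above 480 ms.

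The cost is one sentence of protocol text and an occasional delay for a reading that proves unconfirmed. If the deadline is met and the re-reading clears the patient, that delay is at most about 7 days of a 28-day interval (7/28 = 25%).

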### Hepatic Safety

- Patients who develop increased transaminase levels will be monitored with a second liver function evaluation to confirm the finding. If the finding is confirmed, the patient will be followed with weekly liver function monitoring (AST, ALT, bilirubin levels, Alkaline phosphatase) until values return to pre-treatment levels.
- If any of the criteria below are observed at any scheduled or unscheduled visit the sponsor will perform a follow up within **72 hours** of awareness of the abnormality:
  - ALT or AST > 3 x ULN and Total Bilirubin  $\geq$  2 x ULN
  - ALT or AST > 5 x ULN and  $\leq$  8 x ULN
  - ALT or AST > 8 x ULN
- Hepatic Safety Follow up:
  - Perform liver-directed medical history and physical examination (i.e. assess occupational hazards, concomitant medications including over-the-counter medications, inter-current illness, etc.)
  - Liver chemistry tests: ALT, AST, total bilirubin, (fractionate to direct/indirect bilirubin if total bilirubin is > 2.0 x ULN), Albumin, PT (INR), ALP, and GGT. These tests will be monitored every **3-4 days** until resolution or return to baseline status.
  - Perform hepatitis screen: anti-HAV, IgM (to confirm acute hepatitis A), HbsAg, Anti-HBc, anti-HCV (if positive, PCR viral load should be assessed), Anti-HEV, ANA antibodies, anti-smooth muscle anti-bodies, CMV and EBV
  - Perform abdominal ultrasound (liver and biliary tree)
- Patients may need to be discontinued if the abnormal liver function criteria are met upon LFT retesting or immediately discontinued without LFT retesting in the case of ALT or AST > 8 times the upper limit of normal. Progress reports of the event will be maintained until resolution or return to baseline status.
- If any of these criteria are met and deemed an AE by the investigator, the event will be recorded on in the subjects records as well as the adverse event log; if the event is deemed serious by the investigator, then an SAE will be reported (as described below in SAE reporting procedures). In addition, any clinically significant findings from the physical examination will be recorded in the subjects study records and adverse event log.

